3.2 STUDY CALENDAR

Test	Screen	Baseline (Preop)	1 day postop	2 weeks postop	3 months postop	6 months postop	1 year Postop	Annually (M24-M120)
History/Physical examination	x		x	x	x	x	x	x
QOL Questionnaire		x	x	x	x	x	x	M60 and M120
Neck pain		x	x	x		x		
VHI-10		x	x	x		x		
SIS-6		x	x	x		x		
Labs ¹	x		x	x	x	x	x	x
Tg and thyroid antibodies	x				x	x	x	x
Neck USG	x				x	x	x	x
FNA thyroid		x						
Flexible laryngoscopy		x	x ²	As needed		x ³		
Thyroid hormone replacement or suppression therapy			x	x	x	x	x	x

Abbreviated Title: Prophylactic Central Neck Dissection

Version Date: 01/15/2019

Test	Screen	Baseline (Preop)	1 day postop	2 weeks postop	3 months postop	6 months postop	1 year Postop	Annually (M24- M120)
Thyroid hormone withdrawal or recombinant TSH for stim- Tg					x		x ⁶	
DxWBS					x ⁵		x ⁵	
Urine or Serum Pregnancy Test		x						
Advance Directive (NIH only) ⁴		x						

1. Intact PTH, Chemistries including Calcium, albumin, ionized calcium, inorganic phosphorous, thyroid function tests (except on day 1 postoperatively) and other labs as indicated.
2. Flexible laryngoscopy can be performed within 2 weeks after surgery, if it cannot be performed in the first day postoperatively
3. Only if vocal cord abnormalities are found on postoperative day 1 flexible laryngoscopy.
4. As indicated in Section 9.3, all subjects will be offered the opportunity to complete an NIH advance directives form. This should be done preferably at baseline but can be done at any time during the study as long as the capacity to do so is retained. The completion of the form is strongly recommended, but is not required
5. Optional for participating sites

3.3 SURGICAL GUIDELINES

Patients who are randomized to receive TT and pCND will undergo standard TT. pCND will be performed on the ipsilateral side to the dominant tumor by removal of lymphoid and fibrofatty tissue from the hyoid area to the innominate/subclavian vessels and from ipsilateral common carotid sheath medially, including the pretracheal and ipsilateral paraesophageal lymph nodes. If participant has bilateral biopsy-proven PTC, bilateral pCND will be performed in those who are randomized to receive TT and pCND. Care will be taken to preserve the parathyroid glands and their blood supply. If the parathyroid gland is devascularized, it will be autotransplanted into the sternocleidomastoid muscle pocket.

Abbreviated Title: Prophylactic Central Neck Dissection

Version Date: 01/15/2019

Uniform postoperative care and monitoring will be provided to participants in both groups equally.

3.3.1 Postoperative Care

3.3.1.1 Postoperative day 1, participants will be seen in-house and will:

- a. Fill out the following questionnaires.
 - QOL using SF-36 v2 questionnaire
 - Neck pain (scale 0 (no pain) to 10 (unimaginable, unspeakable pain))
 - Voice quality using Voice Handicap Index-10 questionnaire
 - Swallowing symptoms using Swallowing Impairment Score (SIS-6) questionnaire
- b. Undergo flexible laryngoscopy to assess vocal cord functions. This can be performed within 2 weeks postoperatively, if it cannot be done on the first postoperative day.
- c. Receive laboratory evaluation at 6 hours postoperatively and AM of postoperative day 1 which includes Calcium total, Ionized Calcium, Magnesium total (Mg), Inorganic Phosphorus, and intact PTH.
- d. Receive thyroid replacement therapy per standard of care.

3.3.1.2 Two weeks postoperatively (\pm 2 days), participants will be seen in clinic and will

- a. Fill out the following questionnaires.
 - QOL using SF-36 v2 questionnaire
 - Neck pain (scale 0 (no pain) to 10 (unimaginable, unspeakable pain))
 - Voice quality using Voice Handicap Index-10 questionnaire
 - Swallowing symptoms using Swallowing Impairment Score (SIS-6) questionnaire
- b. Receive laboratory evaluation prior to a clinic visit which includes Sodium (Na), Potassium (K), Chloride (Cl), Total CO₂ (bicarbonate), Creatinine, Glucose, Urea nitrogen (BUN), Albumin, Calcium total, Ionized Calcium, Magnesium total (Mg), Inorganic Phosphorus, and intact PTH.
- c. Have index tumor from pathology specimen tested for *BRAF* V600E mutation in either the Clinical Center Laboratory or the laboratory of the participating site
- d. Undergo flexible laryngoscopy, if clinically indicated.
- e. Receive TSH suppression therapy, if indicated, per standardized protocol (
- f. **Table 2**)

3.3.1.3 Three months postoperatively (\pm 2 weeks)

- To assess the primary endpoint of the study, all participants will be seen in clinic, and will either receive recombinant TSH injections or start thyroid hormone withdrawal.
- Participants will be evaluated by endocrinology service for stim-Tg measurement and DxWBS per standardized protocol (optional in patients enrolled at non-NIH site):

Abbreviated Title: Prophylactic Central Neck Dissection

Version Date: 01/15/2019

- a. Laboratory evaluation includes: (stimulated) Tg, anti-thyroglobulin antibodies, TSH, FT4, T3, Calcium total, Ionized Calcium, Magnesium total (Mg), Inorganic Phosphorus, and intact PTH.
- b. DxWBS or RAI with post therapy scan will be performed as needed. If DxWBS is indicated patients should start and maintain a low iodine diet two weeks prior to the scan.
- c. Baseline neck USG.
- d. QOL using SF-36 v2 questionnaire

3.3.1.4 Six months postoperatively (\pm 2 weeks), participants will be seen in clinic and will

- a. Fill out the following questionnaires.
 - QOL using SF-36 v2 questionnaire
 - Neck pain (scale 0 (no pain) to 10 (unimaginable, unspeakable pain))
 - Voice quality using Voice Handicap Index-10 questionnaire
 - Swallowing symptoms using Swallowing Impairment Score (SIS-6) questionnaire
- b. Undergo flexible laryngoscopy only if there were impaired vocal cord function(s) on postoperative day 1 or 2.
- c. Receive laboratory evaluation which includes CBC with differential, Sodium (Na), Potassium (K), Chloride (Cl), Total CO₂ (bicarbonate), Creatinine, Glucose, Urea nitrogen (BUN), Albumin, Calcium total, Ionized Calcium, Magnesium total (Mg), Inorganic Phosphorus, TSH, FT4, T3, Tg, anti-thyroglobulin antibodies, and intact PTH.
- d. Undergo soft tissue neck USG. Any suspicious lymph node(s) or lesion(s) will be biopsied for cytology and Tg wash.

3.3.1.5 One year postoperatively (\pm 2 weeks) for participants who do not receive remnant ablation **or one year post-remnant ablation**, they will be seen in clinic and

- a. Participants who undergo remnant ablation will either receive recombinant TSH for 2 consecutive days or will undergo thyroid hormone withdrawal for 4 weeks, followed by laboratory evaluation. Participants who do not undergo remnant ablation will receive only recombinant TSH for 2 consecutive days, followed by laboratory evaluation which includes Sodium (Na), Potassium (K), Chloride (Cl), Total CO₂ (bicarbonate), Creatinine, Glucose, Urea nitrogen (BUN), Albumin, Calcium total, Ionized Calcium, Magnesium total (Mg), Inorganic Phosphorus, TSH, FT4, T3, Tg (stimulated), anti-thyroglobulin antibodies. Recombinant TSH-stimulated thyroglobulin is optional in patients enrolled at non-NIH site.
- b. Iodine free 24hr urine collection
- c. DxWBS will be performed in all participants enrolled at NIH Clinical Center and is optional in patients enrolled at non-NIH site. Patients must start and maintain a low iodine diet two weeks prior to the scan.

Abbreviated Title: Prophylactic Central Neck Dissection

Version Date: 01/15/2019

- d. All participants will undergo soft tissue neck USG. Any suspicious lymph node(s) will be biopsied if clinically indicated.
- e. Participant who develops elevated unstimulated or stimulated Tg with or without suspicious neck lesion on USG will undergo metastatic work up per 2009 ATA guidelines (11) (**Appendix F**).
- f. QOL using SF-32 v2 questionnaire.

3.3.2 Recurrent Disease

Surveillance for persistent or recurrence disease will be performed every year for 10 years. The study blind will be broken after the 10 year visit unless medically necessary for the patient's continued care. Work up includes:

- a. Detailed history and physical examination in clinic.
- b. Calcium total, Ionized Calcium, Magnesium total (Mg), Inorganic Phosphorus, TSH, Tg (while on levothyroxine), anti-thyroglobulin antibodies.
- c. Soft tissue neck USG.
- d. Other radiographic imaging or nuclear scintigraphy as clinically indicated.
- e. QOL using SF-36 v2 questionnaire will be assessed at 5 and 10 years postoperatively.

3.3.3 Off Study Criteria

- Absence of thyroid cancer in final pathology
- Participant requests to be withdrawn from study
- Completion of 10-year assessment
- Lost to follow-up
- Investigator discretion
- Screen failure
- Death

3.3.4 Off Protocol Therapy and Off-Study Procedure

Authorized staff must notify Central Registration Office (CRO) when a subject is taken off protocol therapy and when a subject is taken off-study. A Participant Status Updates Form from the web site (<http://home.ccr.cancer.gov/intra/eligibility/welcome.htm>) main page must be completed and sent via encrypted email to: NCI Central Registration Office [contact].

For participating sites:

The Participant Status Updates Form will be supplied by the CCR study coordinator. Send the completed form to the CCR study coordinator.

Abbreviated Title: Prophylactic Central Neck Dissection

Version Date: 01/15/2019

4 BIOSPECIMEN COLLECTION

4.1 CORRELATIVE STUDIES FOR RESEARCH

Patients will be co-enrolled on protocol 09-C-0242. Biospecimens will be collected as specified in protocol 09-C-0242.

For participating sites:

Biospecimens will not be collected at participating sites.

5 DATA COLLECTION AND EVALUATION

5.1 DATA COLLECTION

The PI at each site will be responsible for overseeing entry of data into a password protected electronic system (NCI C3D) and ensuring data accuracy, consistency and timeliness. Clinical data will be entered into the NCI C3D at least once every two weeks when patients are enrolled on the trial. Protocol-specific eCRFs will be developed for this trial in C3D. The principal investigator, associate investigators/research nurses and/or a contracted data manager will assist with the data management efforts. All data obtained during the conduct of the protocol will be kept in secure network drives or in approved alternative sites that comply with NIH security standards. Primary and final analyzed data will have identifiers so that research data can be attributed to an individual human subject participant.

The NCI investigators will be responsible for the collection, maintenance, and quality control of the study data.

End of study procedures: Data will be stored according to HHS, FDA regulations and NIH Intramural Records Retention Schedule as applicable.

Loss or destruction of data: Should we become aware that a major breach in our plan to protect subject confidentiality and trial data has occurred, the IRB will be notified.

5.1.1 Data Quality Assurance

The research team will monitor each patient's dataset throughout the study. Source document review will be made against entries on the eCRF and a quality assurance check will be performed to ensure that the investigator is complying with the protocol and regulations. In addition, after the research team (data managers) completes the CRFs a research nurse or physician at the NCI will review and verify the data.

5.2 DATA SHARING PLANS

5.2.1 Human Data Sharing Plan

What data will be shared?

I will share human data generated in this research for future research as follows:

- Coded, linked data in an NIH-funded or approved public repository.
- Coded, linked data in BTRIS (automatic for activities in the Clinical Center)

Abbreviated Title: Prophylactic Central Neck Dissection

Version Date: 01/15/2019

- Identified or coded, linked data with approved participating sites under appropriate agreements.

How and where will the data be shared?

Data will be shared through:

- An NIH-funded or approved public repository, clinicaltrials.gov
- BTRIS (automatic for activities in the Clinical Center)
- Publication and/or public presentations.

When will the data be shared?

- Before publication.
- At the time of publication or shortly thereafter.

5.3 TOXICITY CRITERIA

The following adverse event management guidelines are intended to ensure the safety of each patient while on the study. The descriptions and grading scales found in the revised NCI Common Terminology Criteria for Adverse Events (CTCAE) version 4.0 will be utilized for AE reporting. All appropriate treatment areas should have access to a copy of the CTCAE version 4.0. A copy of the CTCAE version 4.0 can be downloaded from the CTEP web site (http://ctep.cancer.gov/protocolDevelopment/electronic_applications/ctc.htm#ctc_40).

6 SAFETY REPORTING REQUIREMENTS/DATA AND SAFETY MONITORING PLAN

No experimental treatments or procedures are performed as a part of this protocol and therefore no adverse events are expected. In the unlikely event that an adverse event occurs that is attributable to the research, CTCAE v. 4.0 will be used for grading such events. Patients who meet the standard of care criteria for resection of their disease will undergo a major operative procedure and may receive extensive care in the ICU. The principal investigator or designee will closely monitor and document the clinical care and treatment of each patient as per standard of care at the NIH Clinical Center. As per NIH Clinical Center standards of practice, the Occurrence Reporting System will be used to report any clinical events meeting these reporting criteria.

6.1 DEFINITIONS

6.1.1 Adverse Event

Any untoward medical occurrence in a human subject, including any abnormal sign (for example, abnormal physical exam or laboratory finding), symptom, or disease, temporally associated with the subject's participation in research, whether or not considered related to the subject's participation in the research.

Abbreviated Title: Prophylactic Central Neck Dissection

Version Date: 01/15/2019

6.1.2 Suspected adverse reaction

Suspected adverse reaction means any adverse event for which there is a reasonable possibility that the research procedure caused the adverse event. For the purposes of safety reporting, ‘reasonable possibility’ means there is evidence to suggest a causal relationship between the research procedure and the adverse event. A suspected adverse reaction implies a lesser degree of certainty about causality than adverse reaction, which means any adverse event caused by a research procedure.

6.1.3 Unexpected adverse reaction

An adverse event or suspected adverse reaction is considered “unexpected” if it is not consistent with the risk information described in the general investigational plan or elsewhere in the current application.

6.1.4 Serious

An Unanticipated Problem or Protocol Deviation is serious if it meets the definition of a Serious Adverse Event or if it compromises the safety, welfare or rights of subjects or others.

6.1.5 Serious Adverse Event

An adverse event or suspected adverse reaction is considered serious if in the view of the investigator or the sponsor, it results in any of the following:

- Death,
- A life-threatening adverse drug experience
- Inpatient hospitalization or prolongation of existing hospitalization
- Persistent or significant incapacity or substantial disruption of the ability to conduct normal life functions
- A congenital anomaly/birth defect.
- Important medical events that may not result in death, be life-threatening, or require hospitalization may be considered a serious adverse drug experience when, based upon appropriate medical judgment, they may jeopardize the patient or subject and may require medical or surgical intervention to prevent one of the outcomes listed in this definition.

6.1.6 Disability

A substantial disruption of a person’s ability to conduct normal life functions.

6.1.7 Protocol Deviation (NIH Definition)

Any change, divergence, or departure from the IRB-approved research protocol.

6.1.8 Non-compliance (NIH Definition)

The failure to comply with applicable NIH Human Research Protections Program (HRPP) policies, IRB requirements, or regulatory requirements for the protection of human research subjects.

Abbreviated Title: Prophylactic Central Neck Dissection

Version Date: 01/15/2019

6.1.9 Unanticipated Problem

Any incident, experience, or outcome that:

- Is unexpected in terms of nature, severity, or frequency in relation to
 - (a) the research risks that are described in the IRB-approved research protocol and informed consent document; Investigator's Brochure or other study documents, and
 - (b) the characteristics of the subject population being studied; **AND**
- Is related or possibly related to participation in the research; **AND**
- Suggests that the research places subjects or others at a *greater risk of harm* (including physical, psychological, economic, or social harm) than was previously known or recognized.

6.2 NIH INTRAMURAL IRB AND CLINICAL DIRECTOR REPORTING

6.2.1 NIH Intramural IRB and NCI CD Expedited Reporting of Unanticipated Problems and Deaths

The Protocol PI will report in the NIH Problem Form to the NIH Intramural IRB and NCI Clinical Director:

- All deaths, except deaths due to progressive disease
- All Protocol Deviations
- All Unanticipated Problems
- All non-compliance

Reports must be received within 7 days of PI awareness via iRIS.

6.2.2 NIH Intramural IRB Requirements for PI Reporting at Continuing Review

The protocol PI will report to the NIH Intramural IRB:

1. A summary of all protocol deviations in a tabular format to include the date the deviation occurred, a brief description of the deviation and any corrective action.
2. A summary of any instances of non-compliance
3. A tabular summary of the following adverse events:
 - All Grade 2 **unexpected** events that are possibly, probably or definitely related to the research;
 - All Grade 3 and 4 events that are possibly, probably or definitely related to the research;
 - All Grade 5 events regardless of attribution;
 - All Serious Events regardless of attribution.

NOTE: Grade 1 events are not required to be reported.

6.3 NCI GUIDANCE FOR REPORTING EXPEDITED ADVERSE EVENTS FOR MULTI-CENTER TRIALS

The site PI must immediately report to the coordinating center PI any serious adverse event, whether or not considered treatment related, including those listed in the protocol and must include an assessment of whether there is a reasonable possibility that the treatment caused the event within 24 hours of PI awareness of the event. The site PI will use CCR Problem report form ([Appendix I](#)). The Site PI must also report any protocol deviations to the coordinating center PI within 7 days of PI awareness. Participating centers must also submit the report to their IRB in accordance with their institutional policies.

6.4 DATA AND SAFETY MONITORING PLAN

6.4.1 Principal Investigator/Research Team

The clinical research team will meet on a regular basis when patients are being actively treated on the trial to discuss each patient. Decisions about dose level enrollment and dose escalation if applicable will be made based on the toxicity data from prior patients.

All data will be collected in a timely manner and reviewed by the principal investigator or a lead associate investigator. Adverse events will be reported as required above. Any safety concerns, new information that might affect either the ethical and or scientific conduct of the trial, or protocol deviations will be immediately reported to the IRB using iRIS.

The principal investigator will review adverse event and response data on each patient to ensure safety and data accuracy. The principal investigator will personally conduct or supervise the investigation and provide appropriate delegation of responsibilities to other members of the research staff.

6.4.2 Data Safety Monitoring Board (DSMB)

This protocol requires monitoring by the NCI CCR Data Safety Monitoring Board (DSMB) as described in Section [7](#). Interim outcome results will not be revealed to the investigators of the trial; results will be presented to the investigators prior to final accrual to the trial only if the DSMB recommends early termination of the trial.

7 STATISTICAL CONSIDERATIONS

The primary goal of this study is to determine if there is a difference in biochemical cure rates based on postoperative stimulated thyroglobulin levels (stim-Tg) at 3 months, primarily focusing on the rates of athyroglobulinemia, in patients with clinically node negative PTC undergoing TT and with and without pCND. Serum Tg, especially when TSH-stimulated, is a very sensitive and specific marker for residual thyroid tissue, persistent or recurrent differentiated thyroid cancer of follicular cell origin, in the absence of anti-Tg antibodies. Because patients with differentiated thyroid cancer whose Tg and/or stim-Tg becomes undetectable after treatment(s) are typically considered free of disease in the absence of radiographic evidence of tumor, we use athyroglobulinemia as a surrogate for biochemical remission. We conservatively estimate that there should be at least a 20% higher rate of athyroglobulinemia in patients undergoing TT and pCND ($\theta_2 = 0.4$) compared to TT alone ($\theta_1 = 0.2$) during early postoperative period. With a total of 180 evaluable participants (approximately n=90 for each arm) who have no anti-thyroglobulin

Abbreviated Title: Prophylactic Central Neck Dissection

Version Date: 01/15/2019

antibody, the trial will have 80% power ($\beta=0.20$) to detect the difference between 0.2 and 0.4 using a Fisher's exact test with two-sided significance level (α) of 0.05.

The protocol will not have any stratification at the time of randomization because there are no known factors associated with athyroglobulinemia. Because this study only enrolls patients with low-risk PTC, it is unlikely that there would be many patients with advanced age and advanced PTC that may be unevenly distributed which may confound with the results of the study.

This study will be monitored by the NCI/CCR Data Safety and Monitoring Board, both for toxicity as well as efficacy and futility with respect to the primary endpoint.

Beginning in the first spring after twenty total patients have been randomized and treated on the trial, the study will be monitored by the DSMB on an annual basis to evaluate the safety of the two arms. The SAEs (typically grade 3 toxicities, or greater) will be reported according to type of toxicity, and maximal grade noted per patient, for toxicities with at least a possible attribution to the therapy provided on that arm. Comparisons will be made between the two arms using a Cochran-Armitage test for trend, or other appropriate methods, to determine if there is increased toxicity associated with either arm.

In addition, at the first DSMB meeting held following the point at which half of the required total subjects have been enrolled and evaluated, an interim evaluation for greater than expected difference in fractions with athyroglobulinemia will be performed. Specifically, after 90 total patients who do not have anti-thyroglobulin antibody have been evaluated, using an O'Brien-Fleming approach, if the two-tailed p-value for a comparison of the two rates is <0.0054 , then the trial will be stopped at that time and a significant difference declared. While invoking this boundary at an interim point will technically require that the final p-value be 0.0492 or less for the overall significance level to be retained at a 0.05 level, as a practical matter, $p<0.05$ will still be required to declare a significant result.

In addition, a single interim evaluation for futility will also take place after 90 evaluable patients accrued. At the same DSMB meeting as the single interim evaluation for efficacy, the study will be evaluated for futility as follows: if the fraction with athyroglobulinemia on the arm with TT + pCND is identical to or lower than that of the TT alone arm, then accrual will stop because of very small probability of achieving a statistically significant difference in favor of the combination arm if the trial were to be completed.

Data on QOL, swallowing and pain will be collected at baseline and at several postoperative time points indicated using the tools described in the protocol. Changes from baseline to the postoperative values will be determined, normally by subtraction, and the resulting changes over time will be compared between the two randomized arms using appropriate non-parametric tests such as a Wilcoxon rank sum test. Other statistical methods may be used as appropriate for the data obtained. As these are secondary evaluations, the results will not be formally adjusted for multiple comparisons, but any results with p-values <0.05 may be interpreted as needed in the context of the number of such tests being performed.

The trial will have an accrual ceiling of 225 participants in order to allow for a 20% rate of patients with PTC that have anti-thyroglobulin antibody,⁸⁶⁻⁸⁸ which limits the use of postoperative Tg and stim-Tg and thus cannot be included in the 180 required for evaluation. It is anticipated that accrual time will be approximately 6 to 7 years as the investigators currently

Abbreviated Title: Prophylactic Central Neck Dissection

Version Date: 01/15/2019

perform 25-30 cases of preoperative suspicious or confirmed PTC per year and anticipate a higher accrual rate once the protocol is open and publicized.

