1. INTRODUCTION

1.1 STUDY OBJECTIVES

1.1.1 Primary Objective:

- To determine biochemical cure rates in patients with low-risk PTCs undergoing total thyroidectomy (TT) with and without pCND as measured by postoperative TSH-stimulated serum thyroglobulin (stim-Tg) at 3 months (prior to RAI treatment).

1.1.2 Secondary Objectives:

- To determine biochemical cure rates in patients with low-risk PTCs undergoing total thyroidectomy (TT) with and without pCND as measured by postoperative TSH-stimulated serum thyroglobulin (stim-Tg) at 1 year postoperatively in patients who will not receive RAI or 1 year post remnant ablation.
- To determine the following outcome measures in patients undergoing TT with and without pCND:
 - a. The QOL of patients with low-risk PTCs undergoing TT and pCND to those undergoing TT alone using the SF-36v2 standardized questionnaire (preoperative, postoperative day 1, 2 weeks, 3 and 6 months, 1, 5 and 10 years postoperatively).
 - b. Neck pain (preoperative, postoperative day 1, 2 weeks, and 6 months postoperatively).
 - c. Subjective voice quality, swallowing impairment (preoperative, postoperative day 1, 2 weeks, and 6 months postoperatively) as well as objective vocal cord dysfunction (preoperative and postoperative day 1 and 6 months postoperatively only if abnormality is found on postoperative day 1) and requirement for intervention.
 - d. Rate and duration of both symptomatic and asymptomatic hypoparathyroidism including requirement and duration of postoperative oral or IV calcium replacement as well as vitamin D analogue for hypoparathyroidism (preoperative PTH, postoperative day 1, 2 weeks and 6 months postoperatively).
 - e. Rate of cervical wound complications (hematoma, seroma, and surgical site infection) and intervention(s) required.
 - f. The use of radioactive iodine.
 - g. Oncologic outcome:
 - I. Radiographic evidence with biopsy or pathology proven recurrent disease.
 - II. Thyroid cancer-related death.
 - h. The impact of BRAF V600E mutation status on lymph node metastasis in patients with low-risk PTC undergoing TT with or without pCND. In addition, we will compare the rate of disease recurrence in patients undergoing pCND to those who will not undergo pCND, by BRAF V600E mutation status.

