9.5 RISKS/BENEFITS ANALYSIS FOR ALL PATIENTS

The main risk of participation is related to the risk of complications from pCND. The addition of pCND to thyroidectomy is still considered a safe procedure with less than 1% of major complications. The transient hypoparathyroidism can occur up to 25% of patients undergoing TT and pCND, most patients are asymptomatic once the calcium replacement therapy is optimized. Permanent hypoparathyroidism following pCND occurs less than 1%. The benefit of pCND in addition to TT may include a reduction in disease recurrence.

Patients who receive TT and pCND may be upstaged and be more likely to receive RAI due to the discovery of a subclinical lymph node metastasis. The risks of RAI include temporary dry mouth, dry eyes, loss or change of taste, and may have increased risk of second primary cancers in young adults. (92) However, the benefits would outweigh the risks in participants at risk for recurrence.

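### Operated patients without cancer go off study although other text promises 6-month harm data for all; and the board's by-arm safety report is specified for SAEs only

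*Combined protocol and SAP*

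**What the plan says.** **Follow-up of harms.** Section 1.1.2 (c to e) makes three surgical harms secondary outcomes: "objective vocal cord dysfunction", wound complications, and "Rate and duration of both symptomatic and asymptomatic hypoparathyroidism". Section 3.3.1.4 schedules a 6-month visit with calcium, PTH, voice, swallowing and pain scores, and laryngoscopy if the early examination was abnormal. The Précis says that all participants have PTH and calcium at 6 months, and that patients with hypoparathyroidism have PTH and electrolytes followed until it clears.

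Section 3.3.3 lists a final pathology without thyroid cancer among the reasons for going off study. Section 3.3.4 then asks only for notification and a status form.

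**Board review.** Section 7 has the board monitor the trial "both for toxicity as well as efficacy and futility with respect to the primary endpoint". Its annual safety report is specified as follows: "The SAEs (typically grade 3 toxicities, or greater) will be reported according to type of toxicity", by maximal grade per patient, "for toxicities with at least a possible attribution to the therapy provided on that arm", with a comparison between arms. Section 6.4.2 refers back to Section 7 and adds no further harm listing.

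Section 9.5 gives the expected frequency of one of the named harms: "The transient hypoparathyroidism can occur up to 25% of patients undergoing TT and pCND", with most patients free of symptoms once calcium replacement is adjusted.

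**The concern.** Whether prophylactic dissection raises complication rates is one of the open questions that the Précis gives for running the trial. A patient who turns out to have no cancer has still had the randomised operation. That patient's hypoparathyroidism, cord function and swallowing at 6 months tell as much about the added dissection as anyone else's. If the off-study rule is applied when pathology is reported, the randomised comparison of later harms is made on fewer patients than were operated on. The duration of hypoparathyroidism, which is part of the stated outcome, cannot be read from day 1 and 2-week values alone.

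The second concern is smaller. The board can stop the trial for efficacy after 90 evaluable patients (two-tailed p below 0.0054). The by-arm safety table planned for it need not contain the most frequent complication for which the protocol gives a rate, unless a case is serious.

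**Working it through.** **1. Passages side by side.** The Précis text on 6-month tests is not limited by pathology result. Section 3.3.3 is not limited by surgery having taken place. Nothing says which prevails. The Précis text, if it prevails, covers PTH, calcium and electrolytes only. No passage keeps an off-study patient in the 6-month laryngoscopy or the voice, swallowing and pain scores.

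**2. Timing.** No removal date is stated. Section 3.3.1.2 has the index tumour from the surgical specimen tested around the 2-week visit, so pathology is probably known by then. Exit before 6 months is therefore likely but inferred. Day 1 data, and probably 2-week data, would be kept.

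**3. How many patients.** The accrual ceiling reproduces: 180 / (1 − 0.20) = 225, about 112 per arm. The Bethesda table in Appendix D puts malignancy at 60-75% for suspicious and 97-99% for malignant cytology, so 25-40% and 1-3% have no cancer. With m the share entering on suspicious cytology (not stated) and the rest on malignant cytology:

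exits = 225 × [m × (0.25 to 0.40) + (1 − m) × (0.01 to 0.03)]

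| m (assumed) | Exits of 225 |
|---|---|
| 0 | 2.3 to 6.8 |
| 0.25 | 15.8 to 27.6 |
| 0.50 | 29.3 to 48.4 |
| 1 | 56.3 to 90 |

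The third entry route is indeterminate cytology with a mutation. Section 1.2.2 puts the malignancy risk with BRAF V600E at 100%, so I assume no exits by this route. If it supplies 25% of entrants, the middle rows become 15.2 to 25.9 and 28.7 to 46.7, little changed.

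**4. Loss of precision at 6 months.** Interval width scales as √(225 / (225 − x)):
- x = 16: √(225/209) = 1.038
- x = 48: √(225/177) = 1.127
- at the extremes, x = 2 gives 1.004 and x = 90 gives 1.291

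If no permanent case were seen in the dissection arm, the one-sided 95% upper bound is 1 − 0.05^(1/n). It is 2.6% at n = 112, 2.8% at n = 104 (8 exits) and 3.3% at n = 88 (24 exits). Section 9.5 puts permanent hypoparathyroidism below 1%, so fewer than 0.08 to 0.24 permanent cases (8 to 24 × 0.01) would be missed in that arm. At the 25% ceiling, up to 2 to 6 transient cases would have no 6-month reading.

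**5. Board report.** At the Section 9.5 ceiling, 0.25 × 112 = 28 patients in the dissection arm could have transient hypoparathyroidism. The share s that would be serious is not given. The number outside the SAE comparison is 28 × (1 − s): 26.6, 25.2, 21 or 14 for an assumed s of 5%, 10%, 25% or 50%. These are ceilings under an assumed share, not forecasts.

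**6. Other routes to the board.** The tables in Section 6.2.2 go to the IRB and are not described as by arm. At grade 2 they take only unexpected related events, and grade 1 is not required. Section 7 also plans between-arm tests of QOL, swallowing and pain changes, but does not link them to the board. It names no method for hypoparathyroidism, cord function or wound complications.

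**The case against.** Much of the case on the other side stands.

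- The harms are collected in both arms and remain secondary outcomes. The board point concerns what is seen each year during the trial, not what is finally known.
- Serious cases do reach the board. The definition in Section 6.1.5 includes "Inpatient hospitalization or prolongation of existing hospitalization", and the wording in Section 7 is loose enough for the board to ask for more. Concentrating on serious, possibly attributable events is a defensible choice when both operations are described as standard of care.
- A reader might infer that an SAE-only comparison could hardly show a difference, because Section 9.5 puts major complications below 1%. The documents do not support that. Serious adverse events are defined more widely than major complications, and no SAE rate is given.
- A reader might also infer that patients without cancer have no 6-month safety provision at all. The Précis text on 6-month PTH and calcium, and on following hypoparathyroidism until it clears, is not restricted by pathology. The fair statement is a conflict to be reconciled, plus a gap for laryngoscopy and the questionnaires.
- The counts in steps 3 and 5 depend on shares that the documents do not give. The full range of 2 to 90 exits says little by itself.

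What remains is that the off-study rule, as written, can drop randomised and operated patients from a harm comparison to which they fully belong, and that the planned board table omits non-serious cases of the protocol's own harm outcomes.

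**Conclusion.** The point holds at modest size. The main part is the conflict between Section 3.3.3 and the Précis, together with the absence of any text keeping operated patients without cancer in the 6-month laryngoscopy, voice, swallowing and pain assessments. If 25-50% enter on suspicious cytology, and removal falls before month 6, about 16 to 48 patients are affected and 6-month intervals widen by about 4-13%. Both conditions are assumptions.

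A reader might infer a biased comparison of harms. That does not follow: whether a nodule is cancer is settled before randomisation, so exits should be balanced between arms in expectation. The loss is in precision and completeness.

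The board report is a secondary point of low severity. It changes no final result, and the non-serious share of the up to 28 cases is unknown.

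**What to change.** 1. Amend Section 3.3.3, and reconcile it with the Précis, so that operated patients without cancer stay in harm outcome collection through the 6-month visit already scheduled. Leave them out only of the thyroglobulin and recurrence analyses.
2. State in Section 7 that between-arm differences in hypoparathyroidism, vocal cord dysfunction and wound complications will be reported with 95% confidence intervals in all randomised and operated patients.
3. Keep the annual SAE comparison and add one descriptive by-arm table of the same three harms at any grade.

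The cost is a wording change, continued outcome collection to month 6 in a modest number of patients without cancer, and one table from data already collected. The board would read more low-grade events, so the table should be labelled descriptive. The sample size, primary endpoint and stopping boundary are unchanged.
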